7.2. Exclusion Criteria

1. Metastatic uveal or ocular melanoma.
2. Active central nervous system (CNS) metastases or other CNS (e.g., meningeal) involvement.
3. Patients must have resolution or improvement of immune-mediated treatment-related adverse reactions related to prior treatment(s) to Grade ≤ 1 without steroid maintenance therapy or his or her previous baseline prior to the corresponding CPI therapy.
 - a. History of immune-mediated treatment-related adverse reactions leading to discontinuation of prior anti-PD-1, anti-PD-L1, or anti-PD-L2 mAbs or severe hypersensitivity reaction to any mAb or any excipients which in the opinion of the Investigator, precludes future use of anti-PD-1/PD-L1 therapy.
4. Concurrent systemic steroid therapy higher than physiologic dose (> 10 mg/day of prednisone or equivalent).
5. Previous treatment with selinexor or other XPO1 inhibitors.
6. Insufficient time since or not recovered from procedures or anti-cancer therapy, defined as:
 - a. Not recovered from major surgery ≤ 28 days prior to Day 1 dosing. Minor procedures, such as biopsies, dental work, or placement of a port or intravenous (IV) line for infusion are permitted
 - b. Have ongoing clinically significant anti-cancer therapy-related toxicities Common Terminology Criteria for Adverse Events (CTCAE) Grade >1 . In specific cases, patients whose toxicity has stabilized or with Grade 2 non-hematologic toxicities can be allowed following documented approval by the Sponsor's Medical Monitor
 - c. Had last dose of previous anti-cancer therapy ≤ 14 days prior to Day 1 dosing
 - d. Palliative radiotherapy >14 days prior to the study is allowed
 - e. Received investigational drugs in other clinical trials within 28 days, or 5 half-lives of the investigational drug (whichever is shorter), prior to C1D1
7. Live-attenuated vaccine (e.g., nasal spray influenza vaccine) ≤ 14 days prior to the intended C1D1.
8. Impairment of gastrointestinal (GI) function or GI disease that could significantly alter the absorption of selinexor (e.g. vomiting, or diarrhea that is CTCAE v5.0 grade >1).
9. Life expectancy <4 months based on the opinion of the Investigator.

10. Active pneumonitis requiring steroid therapy.
11. Uncontrolled (i.e., clinically unstable) infection requiring parenteral antibiotics, antivirals, or antifungals within 7 days prior to first dose of study treatment; however, prophylactic use of these agents is acceptable (including parenteral).
12. Any life-threatening illness, medical condition, or organ system dysfunction which, in the Investigator's opinion, could compromise the patient's safety, prevent the patient from giving informed consent, or being compliant with the study procedures.
13. Female patients who are pregnant or lactating.
14. Active hepatitis B virus treated with antiviral therapy for hepatitis B within 8 weeks with a viral load >100 IU/mL.
15. Untreated hepatitis C virus positive without documentation of negative viral load per institutional standard.
16. Human immunodeficiency virus positive with CD4+ T-cells \leq 350 cells/uL, positive viral load per institutional standard, and a history of acquired immunodeficiency syndrome - defining opportunist infections in the last year.

7.3. Screen Failures

Screen failures are defined as patients who consent to participate in the clinical study but are not subsequently entered in the study. A minimal set of screen failure information is required to ensure transparent reporting of screen failure patients to meet the Consolidated Standards of Reporting Trials (CONSORT) publishing requirements and to respond to queries from regulatory authorities. Minimal information includes demography, screen failure details, eligibility criteria, and any SAE.

Individuals who do not meet the criteria for participation in this study (screen failure) may be rescreened. Rescreened patients should be assigned the same patient number as for the initial screening.

8. STUDY TREATMENT

8.1. Study Treatment Administered

All study drugs must be dispensed only by a pharmacist or appropriately qualified site staff, including the Investigator.

Table 2: Study Treatment

Treatment Name	Selinexor (Xpovio™)	Pembrolizumab (Keytruda™)
Dose Formulation	Tablet	Solution
Unit Dose Strength	20 mg	25 mg/mL
Dosage Level	80 mg, single dose once weekly	400 mg once every 6 weeks on Day 1
Route of Administration	PO	IV

8.2. Dosing and Administration of Selinexor

8.2.1. Labeling

Medication labels for each blister pack of selinexor will be in the local language and comply with the legal requirements of each country. They will include storage conditions for the drug and the randomization number, but no information about the patient.

8.2.2. Dispensing Directions

The Investigator or responsible site personnel must instruct the patient or caregiver to take the study drug as per protocol. Study drug will be dispensed to the patient by authorized site personnel only. Additional dispensing instructions will be provided in the Pharmacy Manual.

8.2.3. Dosing Information

Selinexor tablets should be taken orally with at least 120 mL (4 fluid ounces) of water. Selinexor can be taken with or without food. In order to avoid contact with skin, tablets must be swallowed whole and should not be crushed.

For additional details on drug formulation, preparation, and administration, please refer to the Pharmacy Manual and the Investigator's Brochure.

8.3. Preparation/Handling/Storage/Accountability

The Investigator or designee must confirm appropriate temperature conditions have been maintained during transit for all study treatment received and any discrepancies are reported and resolved before use of the study treatment.

Only patients enrolled in the study may receive study treatment and only authorized site staff may supply or administer study treatment. All study treatments must be stored in a secure, environmentally controlled, and monitored (manual or automated) area in accordance with the labeled storage conditions with access limited to the Investigator and authorized site staff.

The Investigator, institution, or the head of the medical institution (where applicable) is responsible for study medication accountability, reconciliation, and record maintenance (i.e., receipt, reconciliation, and final disposition records).

Further guidance and information for the final disposition of unused study medications are provided in the Pharmacy Manual.

8.4. Study Treatment Compliance

Patient compliance with study treatment will be assessed at each visit. Deviation(s) from the prescribed dosage regimen should be recorded in the electronic case report form (eCRF).

8.5. Concomitant Medication

Concomitant medications include any prescription or over-the-counter preparation, including blood/blood products, vitamins, dietary supplements, over-the-counter medications, and oral herbal preparations taken during the study. Patients may continue their baseline medication(s). All concomitant medication(s) must be reported in the eCRF. Any diagnostic, therapeutic, or surgical procedure performed during the study period should be recorded, including the dates, description of the procedure(s), and any clinical findings, if applicable.

8.5.1. Prohibited Concomitant Medications

Concurrent therapy with any approved or investigative anticancer therapeutic outside of those included in this study is not allowed. Use of any immunosuppressive agents during the study must be confirmed by the Sponsor. Refer to the full prescribing information for treatment of patients receiving pembrolizumab for the most current information on prohibited concurrent medications.

Elimination of selinexor is in part attributable to CYP3A4-mediated metabolism. Therefore, moderate and strong CYP3A inducer or inhibitor should be used with caution when co-administer with selinexor as it might result in decreased or increased selinexor exposure. A list of strong and moderate CYP3A inhibitors and inducers is provided in [Appendix 3](#).

There are no restrictions on the use of acetaminophen (paracetamol) or acetaminophen-containing products in combination with study drug, except on days of selinexor dosing, when acetaminophen must not exceed a total daily dose of 1 gram.

8.5.2. Permitted Concomitant Medications

Patients will receive concomitant medications as prophylaxis and to treat symptoms, AEs and intercurrent illnesses that are medically necessary as standard care. Medications to treat concomitant diseases like diabetes, hypertension, etc., are allowed. Supportive measures for optimal medical care should be provided to all patients in this study. Supportive care per institutional guidelines and/or the National Comprehensive Cancer Network® (NCCN) Clinical Practice Guidelines in Oncology ([NCCN Guidelines®](#)) should be used as clinically indicated at the discretion of the Investigator. Should the treating physician choose to use different antiemetics than what is described in this section, the treating physician should consult the sponsor in order to ensure two different classes of antiemetics are administered prophylactically. Necessary supportive care such as appetite stimulants, and anti-diarrheals will be allowed.

8.5.2.1. Ondansetron

In order to minimize nausea, unless contraindicated all patients must receive 2 anti-emetics initially: a 5-HT3 (5-hydroxytryptamine 3) antagonist (ondansetron 8 mg or equivalent), starting 30-60 minutes before administration of study drug and continued 2-3 times daily for at least 2 days after dosing, as needed. A neurokinin-1 (NK-1) antagonist or another anti-emetic agent should be used as per the label per NCCN Guidelines Alternative or additional anti-emetic agents may be used if the patient does not tolerate or has inadequate antiemetic effect with 5-HT3 antagonists.

8.6. Nutritional Counselling

Patients should be given documented nutritional consultation or counselling per local practice to discuss any food recommendations and strategies for managing potential nausea and appetite changes experienced with study drug. This must be completed within the Screening period of the study and prior to administration of study drug on C1D1. The Investigator or any study staff can provide the nutritional counselling, in person or by telephone. Nutritional/supportive care is to be provided throughout, as needed, and per local guidance.

8.7. Dose Modification

8.7.1. Selinexor Dose Modifications

All dose modifications will be captured in the eCRF. Dose modifications should be associated in the eCRF with the AE requiring the modification.

If drug-related toxicity requires a treatment delay of more than 28 days, the patient will be taken off study treatment unless the investigator in consultation with the medical monitor believes that it is safe for the patient to resume therapy.

For all Grade ≥ 3 hematological or non-hematological AEs that are NOT selinexor related, after consultation with the Medical Monitor and at the discretion of the Investigator, selinexor dosing may be maintained.

8.7.2. Dose Modifications for Overlapping Toxicities

For general overlapping toxicities, the following guidance is recommended after ruling out alternative causes:

- If the non-hematological toxicity is attributable to selinexor, please follow the recommended management actions for the respective AE type, outlined in Table 5.
- If the toxicity is attributable to pembrolizumab, please refer to the pembrolizumab product insert for the management of the AE.
- The management of overlapping toxicities should include withholding pembrolizumab and starting corticosteroids until the toxicity is Grade ≤ 1 or at baseline before restarting at the next cycle:
 - The corticosteroid dosing for intolerable Grade 2 or Grade 3 toxicities is 0.5-1 mg/kg/day of prednisone or equivalent with a slow taper until the event is back to Grade ≤ 1 .

- For Grade 4 toxicities or recurrent Grade 3 toxicities, the dose of corticosteroids is 1-2 mg/kg/day of prednisone or equivalent with a slow taper over 3-6 weeks until the event is back to Grade ≤ 1
- If the AE recurs again, stop pembrolizumab permanently

Table 3 summarizes the selinexor dose levels for modification; **Table 4** describes supportive care and dose adjustment guidelines for hematologic adverse reactions. **Table 5** describes dose adjustment guidelines for non-hematologic adverse reactions. Deviations from the guidelines are permitted after discussion between the Sponsor and the treating physician.

Table 3: Selinexor Dose Modification Steps for Adverse Reactions

Recommended Starting Dosage	First Reduction	Second Reduction	Third Reduction	Fourth Reduction
80 mg Once weekly	60 mg Once weekly	40 mg Once weekly	20 mg Once weekly	Discontinue

Table 4: Dose Modification for Hematologic Adverse Reactions

Adverse Reaction	Occurrence	Action
Thrombocytopenia		
Platelet count $< 50,000 \mu\text{L}$ (Grade 3-4)	First Occurrence	Hold selinexor until platelets recover to $\geq 75,000$ Restart selinexor at same dose level (see Table 3). Consider additional supportive care and discuss with Sponsor's Medical Monitor
	2 nd and subsequent	Hold selinexor until platelets recover to $\geq 75,000$ Reduce selinexor by 1 dose level (see Table 3). Consider additional supportive care and discuss with Sponsor's Medical Monitor
Platelet count $< 50,000 \mu\text{L}$ with concurrent bleeding	Any	Hold selinexor until platelets recover to $\geq 50,000$ and bleeding has resolved. Restart selinexor at 1 lower dose level (see Table 3) Consider additional supportive care and discuss with Sponsor's Medical Monitor
Neutropenia		
Absolute neutrophil count (ANC) of 0.5 to $1.0 \times 10^9/\text{L}$ (Grade 3)	First Occurrence	Hold selinexor until ANC recover to ≥ 1.0 Restart selinexor at same dose level (see Table 3). Consider additional supportive care and discuss with Sponsor's Medical Monitor

Adverse Reaction	Occurrence	Action
ANC of 0.5 to $1.0 \times 10^9/L$ (Grade 3)	2 nd and subsequent	Hold selinexor until ANC recover to ≥ 1.0 Reduce selinexor by 1 dose level (see Table 3). Consider additional supportive care and discuss with Sponsor's Medical Monitor
ANC $< 0.5 \times 10^9/L$ (Grade 4) OR febrile neutropenia	Any	Hold selinexor until ANC recover to ≥ 1.0 Reduce selinexor by 1 dose level (see Table 3). Consider additional supportive care and discuss with Sponsor's Medical Monitor
Anemia		
Hemoglobin level less than 8.0 g/dL	Any	Administer blood transfusions and/or other treatments per clinical guidelines.
Life-threatening consequences (urgent intervention indicated)	Any	Interrupt selinexor. Monitor hemoglobin until levels return to 8 g/dL or higher. Restart selinexor at 1 dose level lower (see Table 3). Administer blood transfusions and/or other treatments per clinical guidelines.
Overlapping anemia (due to combination of selinexor and pembrolizumab)		Interrupt selinexor Monitor hemoglobin until levels return to ≥ 8 g/dL or baseline Restart selinexor at 1 dose level lower (see Table 3).

^aNational Cancer Institute Common Terminology Criteria for Adverse Events (NCI CTCAE) v5.0.

Table 5: Selinexor Dose Modification Guidelines for Non-hematologic Adverse Reactions

Adverse Reaction ^a	Occurrence	Action
Hyponatremia		
Grade 1 or 2 (sodium level < normal to 130 mmol/L)	Any	Maintain dose Rule out other causes including drug (e.g. diuretic) effects Be certain that reported sodium level is corrected for concurrent hyperglycemia (serum glucose > 150 mg/dL) Treat hyponatremia per institutional guidelines including dietary review Consider addition of salt tablets to patient's diet
Grade 3 (sodium levels 120 to 129 mmol/L) without symptoms	Any	Rule out other causes including drug (e.g., diuretic) effects Be certain that reported sodium level is corrected for concurrent hyperglycemia (serum glucose > 150mg/dL) If (corrected) sodium is Grade \leq 3 and continues to be asymptomatic, then patient may continue current dosing provided that IV saline and/or salt tablets are provided
Grade 3 (sodium levels 120 to 129 mmol/L) with symptoms OR Grade 4 (sodium levels < 120 mmol/L)	Any	Rule out other causes including drug (e.g., diuretic) effects Be certain that reported sodium level is corrected for concurrent hyperglycemia (serum glucose > 150 mg/dL) Interrupt selinexor dosing until resolved to Grade 1 or baseline and without symptoms. Reduce selinexor by 1 dose level
Overlapping hyponatremia Grade 3 or 4 (due to combination of selinexor and pembrolizumab)	Any	Rule out other causes Interrupt selinexor dosing until resolved to Grade 1 or baseline and without symptoms Restart selinexor at 1 dose level lower (see Table 3).
Fatigue		
Grade 2 lasting greater than 7 days OR Grade 3	Any	Interrupt selinexor. Monitor until fatigue resolves to Grade 1 or baseline. Restart selinexor at 1 dose level lower (see Table 3).
Overlapping fatigue (due to combination of selinexor and pembrolizumab)	Any	Interrupt selinexor. Monitor until fatigue resolves to Grade 1 or baseline. Restart selinexor at 1 dose level lower (see Table 3).
Nausea and Vomiting		

Adverse Reaction ^a	Occurrence	Action
Grade 1 or 2 nausea (oral intake decreased without significant weight loss, dehydration or malnutrition) OR Grade 1 or 2 vomiting (5 or fewer episodes per day)	Any	Maintain selinexor and initiate additional anti-nausea medications.
Grade 3 nausea (inadequate oral caloric or fluid intake) OR Grade 3 or higher vomiting (6 or more episodes per day)	Any	
Rule out other causes. Use additional anti-nausea medications to supplement the protocol-required 5-HT3 antagonists
 
In those patients in whom a 5-HT3 antagonist is contraindicated or not sufficient, use of olanzapine (2.5-5.0 mg po once daily in the morning) is recommended based on Investigator experience during Phase 1 selinexor studies. (Additional options can be found in the National Comprehensive Cancer Network (NCCN) Clinical Practice Guidelines in Oncology (CPGO) for antiemesis and anorexia/cachexia (palliative care)).
 
Interrupt selinexor dosing until resolved to Grade \leq 2 or baseline and reduce selinexor by 1 dose level (see Table 3).

Overlapping grade 3 nausea (inadequate oral caloric or fluid intake) OR Grade 3 or higher due to combination of selinexor and pembrolizumab	Any	
Rule out other causes.
 
Interrupt selinexor.
 
Monitor until nausea resolves to Grade \leq 2 or baseline.
 
Restart selinexor at 1 dose level lower (see Table 3).
 
Use additional anti-nausea medications to supplement the protocol-required 5-HT3 antagonists
 
In those patients in whom a 5-HT3 antagonist is contraindicated or not sufficient, use of olanzapine (2.5-5.0 mgpo once daily in the morning) is recommended
 
Additional options can be found in the National Comprehensive Cancer Network (NCCN) Clinical Practice Guidelines in Oncology (CPGO) for antiemesis

Diarrhea		
Grade 2 (increase of 4 to 6 stools per day over baseline)	1 st	Maintain selinexor and institute supportive care.

Adverse Reaction ^a	Occurrence	Action
	2 nd and subsequent	Reduce selinexor by 1 dose level (see Table 3). Institute supportive care.
Grade 3 or higher (increase of 7 stools or more per day over baseline; hospitalization indicated)	Any	Interrupt selinexor and institute supportive care. Monitor until diarrhea resolves to Grade 2 or lower. Restart selinexor at 1 dose level lower (see Table 3).
Overlapping grade 3 or higher diarrhea due to combination of selinexor and pembrolizumab	Any	Interrupt selinexor and institute supportive care. Monitor until diarrhea resolves to Grade 2 or lower. Restart selinexor at 1 dose level lower (see Table 3). If the diarrhea is due to both selinexor and pembrolizumab, initiate steroid therapy and consider infliximab if the diarrhea is Grade ≥ 3
Weight Loss and Anorexia		
Weight loss of 10% to less than 20% OR anorexia associated with significant weight loss or malnutrition	Any	Interrupt selinexor and institute supportive care. Monitor until weight returns to more than 90% of baseline weight. Restart selinexor at 1 dose level lower (see Table 3).
Overlapping anorexia associated with significant weight loss or malnutrition due to combination of selinexor and pembrolizumab	Any	Interrupt selinexor and institute supportive care. Monitor until weight returns to more than 90% of baseline weight. Restart selinexor at 1 dose level lower (see Table 3).
Other Non-Hematologic Adverse Reactions		
Grade 3 or 4	Any	Interrupt selinexor. Monitor until resolved to Grade 2 or lower, restart selinexor at 1 dose level lower (see Table 3).
^a National Cancer Institute Common Terminology Criteria for Adverse Events (NCI CTCAE) v5.0.		

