predominantly nausea, vomiting, diarrhea, fatigue, anorexia and weight loss, and these AEs were assessed as low-grade and manageable with dose modification or supportive care. Hyponatremia (typically asymptomatic), confused state and dizziness have also been reported. On the other hand, hematological AEs including thrombocytopenia, neutropenia and anemia, which can be higher grade, were reported primarily in patients with hematologic malignancies. Any potential overlapping toxicity including fatigue, decreased appetite, diarrhea, nausea, pyrexia, constipation, hyponatremia, and anemia will be monitored closely by careful physical examination and clinical laboratory testing on Days 1, 15, and 29 of Cycles 1 and 2 with dose adjustments as per prespecified dose modifications (see [Table 5](#)). Additional visits to manage AEs and telephone contact are also encouraged based upon the patient's condition.

A summary of the clinical trials, antitumor responses observed, and anticipated AEs of selinexor are found in the Investigator's Brochure.

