11.1.4. Adverse Event Causality

The Investigator will make a judgment regarding the relationship of the AE to study treatment, as defined below.

- Not related: These events will lack a strong temporal relationship of the event to the study treatment, making a causal relationship not reasonably possible. Exposure to other drugs, therapeutic interventions, or underlying conditions may provide a sufficient explanation for the event.
- Related: There is a temporal relationship of the event to the study treatment, and the event is more reasonably explained by exposure to the study treatment than by any other drugs, therapeutic interventions, or underlying conditions.

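### Instructions for toxicities attributed to both drugs are not reconciled between the Section 8.7.2 text and Tables 4 and 5, and the overlapping fatigue and anemia rows have no severity trigger

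*Protocol*

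**What the plan says.** Protocol Section 8.7.2 sorts toxicity by attribution. Non-hematologic toxicity attributed to selinexor goes to Table 5. Toxicity attributed to pembrolizumab goes to its product insert. For overlapping toxicity the text reads: "The management of overlapping toxicities should include withholding pembrolizumab and starting corticosteroids until the toxicity is Grade" 1 or lower, or baseline, with restart at the following cycle. Steroid doses follow in two tiers, the lower introduced by "The corticosteroid dosing for intolerable Grade 2 or Grade 3 toxicities is 0.5-1 mg/kg/day". A further recurrence ends pembrolizumab for good. Nothing in this part tells the site what to do with selinexor.

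The section then introduces Tables 3 to 5. Tables 4 and 5 carry six rows of their own for overlapping events, for example "Overlapping anemia (due to combination of selinexor and pembrolizumab" and "Overlapping fatigue (due to combination of selinexor and pembrolizumab". Each holds selinexor and restarts it one level lower. Only the diarrhea row goes further: "If the diarrhea is due to both selinexor and pembrolizumab, initiate steroid therapy and consider infliximab" at Grade 3 or above.

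Section 4.5 lists the potential overlapping toxicities, anemia among them, and says they will be monitored "with dose adjustments as per prespecified dose modifications". It points to Table 5 alone, although the anemia row is in Table 4.

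On attribution, Section 11.1.4 states: "The Investigator will make a judgment regarding the relationship of the AE to study treatment, as defined below". The categories are related and not related, without separation by drug.

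**The concern.** A site facing an event it attributes to both drugs finds two sets of instructions, each addressing a different drug and neither referring to the other. Nothing states whether they apply together or whether the specific row replaces the general text. Steroids appear in one row of six, which may suggest that they are not expected in the other five, while the 8.7.2 text applies them to overlapping toxicity in general.

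The missing triggers are a separate problem, because they remain even if both sets are meant to apply. A dose rule without a severity threshold can be set off by an event that the ordinary row for the same toxicity would leave alone.

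Safety and tolerability of the combination is a secondary objective. SAP Section 3.4.1 counts patients with dose reductions and interruptions, and SAP Section 5.1.2.1 summarises adverse events leading to them. If those figures depend partly on how a site reads 8.7.2, they are harder to interpret as tolerability of the regimen.

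**Working it through.** No sample-size, power or event figure is involved, so there is nothing to recompute. The check sets the 8.7.2 text beside every overlapping row.

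| Source | Trigger stated | Selinexor | Pembrolizumab | Steroids | Recovery level |
|---|---|---|---|---|---|
| 8.7.2 text | None for withholding; steroid doses start at intolerable Grade 2 | Silent | Withhold | Yes | Grade 1 or lower, or baseline |
| Anemia (Table 4) | None | Hold, one level down | Silent | Silent | 8 g/dL or above, or baseline |
| Hyponatremia (Table 5) | Grade 3 or 4 | Hold, one level down | Silent | Silent | Grade 1 or baseline, no symptoms |
| Fatigue (Table 5) | None | Hold, one level down | Silent | Silent | Grade 1 or baseline |
| Nausea/vomiting (Table 5) | Grade 3 or higher | Hold, one level down | Silent | Silent | Grade 2 or lower, or baseline |
| Diarrhea (Table 5) | Grade 3 or higher | Hold, one level down | Silent | Yes | Grade 2 or lower |
| Anorexia (Table 5) | Significant weight loss or malnutrition; no grade | Hold, one level down | Silent | Silent | Weight above 90% of baseline |

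Across the six rows:
- selinexor held and reduced: 6 of 6;
- pembrolizumab withholding mentioned: 0 of 6;
- steroids mentioned: 1 of 6;
- a CTCAE grade in the trigger: 3 of 6;
- no severity threshold of any kind: 2 of 6 (anemia and fatigue).

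**Fatigue.** The ordinary row acts at "Grade 2 lasting greater than 7 days" or at Grade 3. The overlapping row has no grade and applies at any occurrence. Followed literally, Grade 1 fatigue attributed to both drugs calls for a hold and a one-level reduction. The recovery level is Grade 1 or baseline, so the patient meets trigger and recovery on the same day. Table 3 steps 80, 60, 40, 20 mg and then discontinuation, so four such events would exhaust the ladder.

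**Anemia.** The ordinary row for hemoglobin below 8.0 g/dL gives transfusion or other treatment and no interruption; interruption is tied to life-threatening consequences. The overlapping row has no hemoglobin value and asks for recovery to 8 g/dL or baseline. A patient at 9 g/dL whose anemia is attributed to both drugs would be held and reduced while already above the restart level.

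**Steroids in diarrhea.** The 8.7.2 text gives steroid doses from intolerable Grade 2. The overlapping diarrhea row starts at Grade 3. For intolerable Grade 2 diarrhea attributed to both drugs, the general text supplies a steroid dose and no overlapping row applies.

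**The case against.** The strongest reply is that the two sets do not contradict each other, and a reader who infers a flat contradiction goes too far. The 8.7.2 sentence says what management should include, which leaves room for other actions. Table 5 is by its title selinexor guidance, so silence on pembrolizumab fits its scope. No overlapping row tells the site to continue pembrolizumab or avoid steroids, and the 8.7.2 bullet does not tell it to continue selinexor. The diarrhea row already combines a selinexor hold with steroids. A site can follow both sets. All of this stands.

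The differing recovery grades are likewise no conflict in themselves. Grade 1 or baseline sits in the pembrolizumab and steroid bullet, whereas the Grade 2 levels govern selinexor restart.

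There are also safeguards. The guidance applies after other causes are ruled out, departures are allowed after discussion with the sponsor, and Section 8.5.1 requires sponsor confirmation of immunosuppressive agents. These limit drift between sites. They do not supply the missing default: a case-by-case departure presupposes one clear rule to depart from.

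A reader might also infer from Section 11.1.4 that the rule applied can never be checked. That is too strong. Section 8.7.1 requires dose changes to be recorded and linked to the adverse event, and Section 8.5 requires concomitant medication to be reported, so holds, reductions and steroids should be traceable. What the stated causality item does not show is whether the event was attributed to one drug or both. The eCRF is not among the documents and may hold more.

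None of this answers the fatigue and anemia rows, whose problem lies within the rows themselves.

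**Conclusion.** The point holds as a failure to reconcile, with two rows that do not work as written. The cumulative reading is available but stated nowhere, so sites could act differently; the documents do not show that they will. The fatigue and anemia defect needs no assumption beyond taking the rows literally: both act at lower severity than the corresponding ordinary rows, and both can be triggered and satisfied at once.

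The size is best given as the row counts. It is tempting to convert the 50% fatigue and 60% nausea in Section 4.4 into patients out of 40, but those rates come from a selinexor study in recurrent glioblastoma. The documents give no share of events attributed to both drugs. Section 4.3 says the earlier melanoma study of the combination showed no clear overlapping toxicities, while listing hematologic toxicity, fatigue, nausea and low sodium as attributed to both drugs. Joint attribution therefore occurs, but its frequency is unknown.

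Sample size and error rates are untouched, and both arms follow the same rules. The consequence is for patient management and for the reported dose reductions, interruptions and related adverse events. No view is taken on which clinical rule is right.

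**What to change.** The sponsor should reconcile the Section 8.7.2 text with the six overlapping rows of Tables 4 and 5. For each event the protocol should state:
- whether the text and the row apply together and, if not, which governs;
- which drug or drugs are affected;
- the severity that triggers action, now absent for fatigue and anemia;
- whether steroids are part of the rule and from what severity, including the diarrhea row against the 8.7.2 text;
- the recovery level for each drug.

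The cross-reference in Section 4.5 should also cover Table 4, where the anemia row sits. The clinical content of every entry is for the sponsor to decide.

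As a small addition, Section 11.1.4 and the adverse event eCRF should record causality separately for selinexor and pembrolizumab, since the applicable rule turns on attribution by drug. The SAP could then summarise events attributed to both.

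The cost is an amendment to one section and two tables, a corrected cross-reference, and a causality item split by drug if the eCRF does not already have one. No extra patients or visits are needed.
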